9.5. EFFICACY AND SAFETY VARIABLES

9.5.1. Efficacy and Safety Measurements Assessed and Flow Chart

The primary objective of this phase 2 study is to assess the ocular safety and efficacy of SY-201 Ophthalmic Solution in subjects with DED. The secondary objective is to assess the systemic safety of SY-201 Ophthalmic Solution in subjects with DED.

[Figure 1](#) summarizes the design of the study.

[figure not shown]

Figure 1: Study Schematic

9.5.1.1. Visit and Procedure Schedule

See [Table 1](#) in [Appendix I](#) for a complete visit and procedure schedule.

9.5.1.2. Demographics and Baseline Characteristics

9.5.1.2.1. Demographics and Disease Characteristics

Demographic characteristics including age (years), sex, race, and ethnicity will be collected at Visit 1. Baseline disease characteristics include tCFS score (mNEI scale),

9.5.1.2.2. Medical and Surgical History

Ocular and non-ocular medical history will be collected at Visit 1.

9.5.1.2.3. Prior and Concomitant Medications

For this protocol, a prescription medication is defined as a medication that can be prescribed only by a properly authorized/licensed clinician. Medications to be reported in the electronic case report form (eCRF) are concomitant prescription medications, over-the-counter medications, and supplements.

All medications that the subject has taken 45 days prior to Visit 1 and through Visit 6 or discontinuation from the study will be recorded in the eCRF and the subject chart. The generic name of the drug, dose, route of administration, duration of treatment (including start and stop dates), frequency, indication, and whether or not the medication was taken due to an AE will be recorded for each medication. Prior and concomitant medications (CMs) will be coded using the World Health Organization Drug Dictionary (WHODrug).

AT, whether subject- or study-supplied, is prohibited during the run-in period of the study (Visit 1 to Visit 2). Any subject who violates this policy will not be randomized to treatment and will be discontinued from the study.

Preservative-free AT (Refresh Plus[®]) will be provided for rescue use during the treatment phase of the study (Visits 2 through 6) but limited to ≤ 2 instillations per day. Subjects will be required to record AT use in a diary and return the used and unused AT at clinic Visits 2 through 6; subjects will be queried about AT use at each clinic visit.

Restricted and prohibited prior and comcomitant therapy are outlined in the protocol Section 5.5.1.

9.5.1.3. Efficacy Assessments

9.5.1.3.1. Primary Efficacy Assessment(s)

Corneal staining will be assessed at each in-clinic visit. The modified National Eye Institute (mNEI) scale defines 5 regions (central, superior, temporal, nasal, and inferior) of the eye and assigns a score of 0-4 to each region in increments of 0.5 to assess the severity of corneal staining. The sum of the 5 regions provides the total score.

9.5.1.3.2. Secondary Efficacy Assessments

9.5.1.3.3. Exploratory Efficacy Assessments

Not applicable.

9.5.1.4. Safety Assessments

The safety of SY-201 Ophthalmic Solution will be evaluated using the following assessments, conducted at each in-clinic visit unless otherwise noted.

1. Adverse event (AE) monitoring
2. Safety labs (chemistry and hematology) – Visits 1 and 6
3. Best Corrected Visual Acuity (BCVA)
4. Slit lamp biomicroscopy and external eye exam
5. Intraocular pressure (IOP)
6. Dilated ophthalmoscopy – Visits 1 and 6
7. Drop comfort assessment – Visits 2 and 6

9.5.1.4.1. Adverse Events

An AE is any untoward medical occurrence in a clinical study participant, temporally associated with the use of study intervention, whether or not considered related to the study intervention. An AE can therefore be any unfavorable and unintended sign (including an abnormal laboratory finding), symptom, or disease (new or exacerbated) temporally associated with the use of study intervention.

An AE or suspected adverse reaction is considered “serious” if, in the view of either the Investigator or Sponsor, it results in any of the following outcomes:

- Death
- A life-threatening AE
- Inpatient hospitalization or prolongation of existing hospitalization
- A persistent or significant incapacity or substantial disruption of the ability to conduct normal life functions, or
- A congenital anomaly or birth defect

Important medical events that may not result in death, be life-threatening, or require hospitalization may be considered serious when, based upon appropriate medical judgment, they may jeopardize the subject and may require medical or surgical intervention to prevent one of the outcomes listed in this definition.

Severity of AEs is described with the following scale:

- **Mild:** requires minimal or no treatment and do not interfere with the subject's daily activities
- **Moderate:** results in a low level of inconvenience or concern and may cause some interference with functioning
- **Severe:** interrupts a subject's usual daily activity and may require systemic drug therapy or other treatment. Severe events are usually potentially life-threatening or incapacitating. The term "severe" does not necessarily equate to "serious."

Relationship of adverse events to study intervention is classified according to the following scale:

- **Unrelated:** no reasonable possibility that the administration of the IP caused the event, no temporal relationship between the IP and event onset, or an alternate etiology has been established
- **Related:** is known to occur with the IP, is a reasonable possibility that the IP caused the AE, or there is a temporal relationship between the IP and event. Reasonable possibility means that there is evidence to suggest a causal relationship between the IP and the AE.

9.5.1.4.2. Safety Labs (Chemistry and Hematology)

The following clinical laboratory tests will be performed at Visits 1 and 6.

- Chemistry
 - Sodium, Potassium, BUN, Creatinine, Glucose, Calcium, Phosphorus, Total Protein, Albumin, AST (SGOT), ALT (SGPT), Alkaline Phosphatase, Total Bilirubin, Chloride, Bicarbonate
- Hematology
 - Hemoglobin, Hematocrit, RBC, MCH, MCHC, RDW, WBC, Neutrophils, Lymphocytes, Monocytes, Eosinophils, Basophils, Platelets

9.5.1.4.3. Best Corrected Visual Acuity (BCVA)

The BCVA is measured on both eyes in LogMAR at every in-clinic visit. LogMAR is calculated as Baseline value + (n × 0.02); where the baseline value is the LogMAR number of the last line read (at least one letter read correctly in this line), "n" is the total number of letters missed up to and including the last line read, and "0.02" is the value for each letter.

9.5.1.4.4. Slit Lamp Biomicroscopy and External Eye Exam

The biomicroscopy exam should be performed at every in-clinic visit with the slit lamp using a beam width and intensity that provide optimal evaluation of the anterior segment.

This procedure will be performed in the same manner for all subjects observed at the Investigator's site. The site will record all abnormal or present findings in the source document and the Investigator will evaluate the abnormal or present findings as non-clinically significant (NCS) or clinically significant (CS). CS and NCS abnormal findings will be recorded in the source documentation. However, only CS abnormal descriptions will be captured in the eCRF.

Anterior chamber cells and flare will be graded on 5-point scales. Eyelid hyperemia and edema, corneal edema, and conjunctival edema (chemosis) and discharge/exudate will be graded on a 4-point scale (None, Mild, Moderate, Severe).

Normality for iris, pupil, lashes, lens, and corneal endothelium will be collected.

9.5.1.4.5. Intraocular Pressure (IOP)

Intraocular pressure must be measured by Goldmann Applanation tonometry with every effort to ensure the same examiner using the same tonometer for all visits.

9.5.1.4.6. Dilated Ophthalmoscopy

Dilated ophthalmoscopy will be completed at Visits 1 and 6 and will include assessment of the vitreous, retina, macula, choroid, optic nerve, and vertical optic nerve cup-to-disc ratio. Findings will be graded as normal or abnormal. All abnormalities will be recorded in the source documentation and CS or NCS will be indicated. Clinically significant abnormal findings will be reported in the medical history or adverse event eCRF.

9.5.1.4.7. Drop Comfort Assessment

At Visits 2 and 6, subjects will be asked to rate the comfort of the drop for both eyes as one score at 1 minute and 5 minutes post-dose. Integer scores range from 0 (Comfortable) to 10 (Uncomfortable).

9.5.2. Appropriateness of Measurements

All assessments used in this study are widely used and generally recognized as reliable, accurate, and relevant.

9.5.3. Primary Efficacy Variable(s)

Two primary ocular efficacy endpoints (one sign and one symptom) will be tested sequentially:

- Mean change from baseline (CFB) in total corneal fluorescein staining (tCFS; modified National Eye Institute [mNEI] scale, 0-20)

9.5.4. Drug Concentration Measurements

No drug concentration measurements will be made for this study.

9.6. DATA QUALITY ASSURANCE

Each clinical site will perform internal quality management of study conduct, data and biological specimen collection, documentation, and completion. An individualized quality management plan will be developed to describe a site's quality management.

Quality control (QC) procedures will be implemented beginning with the data entry system and data QC checks that will be run on the database will be generated. Any missing data or data anomalies will be communicated to the site(s) for clarification/resolution.

Following written Standard Operating Procedures (SOPs), the monitors will verify that the clinical trial is conducted and data are generated and biological specimens are collected, documented (recorded), and reported in compliance with the protocol, International Council for Harmonisation (ICH) Good Clinical Practice (GCP), and applicable regulatory requirements (e.g., Good Laboratory Practice [GLP], Good Manufacturing Practice [GMP]).

The investigational site will provide direct access to all trial-related sites, source data/documents, and reports for the purpose of monitoring and auditing by the Sponsor, and inspection by local and regulatory authorities.

9.6.1. Training and Education of Investigators and Study Site Personnel

An Investigator Meeting will be held before study initiation and attended by the Investigators and/or Sub-Investigators from each study site, study coordinators from each study site, if possible, and personnel from the sponsor and the Contract Research Organization (Lexitas Pharma Services, Inc., hereafter referred to as Lexitas). The purpose of this meeting is to train and instruct the Investigators and the study coordinators on the proper conduct of the clinical trial and ensure that all subjects are aware of their obligations set out by the protocol, ICH guidelines, GCP guidelines, and other applicable regulatory requirements.

9.6.2. Monitoring of Study Sites

Lexitas Pharma Services, Inc., will conduct the clinical monitoring for this study. A Clinical Monitoring Plan (CMP) is to be used, which will describe in detail who will conduct the monitoring, at what frequency monitoring will be done, at what level of detail monitoring will be performed, and the distribution of monitoring reports.

This clinical trial will be monitored at regular intervals. All information dealt with during these visits will be treated as strictly confidential. All monitoring and study management will be conducted according to GCP and United States Code of Federal Regulations.

9.6.3. Data Entry and Verification of Database Used for Analysis and Reporting

Data collection is the responsibility of the clinical trial staff at the site under the supervision of the site's Investigator. The Investigator is responsible for ensuring the accuracy, completeness, legibility, and timeliness of the data reported.

Lexitas will review the eCRFs entered by investigational site staff for completeness and accuracy and instruct the investigational site staff to make any required corrections or additions. After data have been entered into the study database, a system of computerized data validation checks will be implemented and applied to the database. Queries will be sent to the investigational site and designated investigational site staff are required to respond to the query and edit data, as necessary. All changes to the study database will be documented.

It is the responsibility of the monitor to make certain that all data are completed on the eCRFs. At the end of each study period, the Investigator will sign and date the eCRF to attest to the authenticity of the collected data and coherence between the data in the eCRF and the data in the source documents.

9.6.4. Clinical Study Report

The final clinical study report will be reviewed, audited, and approved by medical, clinical, statistical, and regulatory staff from the sponsor, and key study contributors from Lexitas.

9.6.5. Inter-Laboratory Standardization Methods

Not applicable. A single, qualified, and certified central clinical laboratory will be used to analyze and report clinical laboratory data.

9.7. STATISTICAL METHODS PLANNED IN THE PROTOCOL AND DETERMINATION OF SAMPLE SIZE

This section of the analysis plan describes the analyses explicitly mentioned in the protocol as well as additional analyses not explicitly mentioned in the protocol but planned prior to breaking the treatment mask. [Section 9.8](#) describes any changes to analyses that were explicitly mentioned in the protocol or statistical analysis plan.

9.7.1. Statistical and Analytical Plans

General Conventions

Summary statistics for the data collected during this study will be presented to give a general description of the subjects studied. Data from all sites will be combined in the computation of these descriptive summaries. Categorical variables will be summarized by the frequency and percentage of subjects in each category. Continuous variables will be summarized using N, mean, standard deviation (SD), median, minimum, and maximum values.

Number of subjects, minimums, and maximums will be calculated to the same number of decimal places as the source data. Means, medians, standard deviations, and quartiles will be calculated to one more decimal place than the source data. Percentages will be calculated to the nearest one decimal place. Zero count cells will be displayed as "0" with percentage of (0%). Unless otherwise noted, summaries will be performed by the treatment group and presented in the order of: SY-201 2.0% or 1.0% or 0.5% (efficacy analyses only), SY-201, 2.0%; SY-201, 1.0%; SY-201, 0.5%; Vehicle.

Statistical tests will be presented as two-sided p-values rounded to four decimal places; p-values less than 0.0001 will be presented as '<0.0001' and p-values = 1 will be presented as '>0.9999' in all tables. Unless otherwise indicated, statistical testing will be carried out at the $\alpha = 0.05$ significance level.

Baseline values will be defined as the last measurement prior to dosing of double-masked study medication. Ocular measurements will use the most recent measurement for each eye.

Numeric laboratory data may be recorded at limits of detection (with a '<' or '>' sign, i.e. < 0.1 or > 0.1). To summarize the data, the original value will be converted to one unit less or more at the level of measured precision (e.g. 0.4 in the case of < 0.5 and to 0.6 in the case of > 0.5). The actual values will be presented in the data listings.

MMP-9 data may be recorded at limits of detection of < 5 ng/mL or > 1000 ng/mL. To summarize the data, the original value will be converted to either 4 ng/mL or 1010 ng/mL, respectively. The actual values will be presented in the data listings.

All data collected in this study will be presented in individual subject data listings for all subjects.

Computations for all results will be performed using SAS (Version 9.4, SAS/STAT 15.2) computer software package (SAS Institute, Inc, 2013, 2020), unless otherwise specified.

Strata and Covariates

For analysis of efficacy endpoints, longitudinal models will model the change from baseline of each endpoint as the dependent variable with the baseline measurement of the corresponding endpoint as a covariate and treatment group as the main effect. A random effect for site will be added to account for site-to-site variability.

Subgroups

Subgroup analyses will include testing of the mean CFB in tCFS,

Subgroup analyses by sex and age group (<65 years, ≥65 years) may also be performed.

Multiplicity

To control for type I error, comparisons will be made within each active dose level of SY-201 Ophthalmic Solution compared to Vehicle. In other words, the primary endpoints will be compared sequentially between SY-201 Ophthalmic Solution 2.0% and Vehicle, first testing tCFS and, if statistically significant, . Should both endpoints achieve statistical significance for the 2.0% dose, testing will proceed to Y-201 Ophthalmic Solution 1.0% versus Vehicle, first testing tCFS and, if statistically significant, . Should both endpoints achieve statistical significance for the 1.0% dose, testing will proceed to SY-201 Ophthalmic Solution 0.5% and Vehicle, first testing tCFS and, if statistically significant, . In other words, the first non-significant result in this testing hierarchy of six hypotheses will imply that subsequent tests are non-significant.

Missing Data and Outliers

Every attempt will be made to capture all study data. All analyses will utilize observed data only. Analysis of continuous efficacy endpoints using MMRM assumes missing at random (MAR). Sensitivity analyses of the primary endpoints will be performed utilizing control-based pattern imputation, last observation carried forward (LOCF), and baseline observation carried forward (BOCF).

Visit Windows

The nominal visits listed in the eCRF will be used in the summaries. In general, unscheduled visits will not be summarized in tables unless otherwise noted.

Missing Dates

Missing dates that occur for prior or concomitant medications or adverse events will be queried for a date. If no date is obtained, the following imputation rules will apply:

- For start dates, if the given year (or year-month) is the same as study drug administration, the start date will be imputed as study drug administration date; otherwise, missing month-day (or day) will be imputed as '01-01' (or '01').
- For stop dates, missing months will be imputed as '12' and missing days will be imputed as the last day of the month. If this creates a date after discontinuation/completion, the date of discontinuation/completion will be used.

Imputed dates will only be used to classify events or medications, such as occurring before or after the start of treatment. Imputed dates will only be used in tables. Listings will display the available date data.

Interim Analysis

There is no unmasked efficacy or futility interim analysis for this study.

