8.2.1 Adverse Events (AEs) and Serious Adverse Events (SAEs)

Adverse events will be monitored throughout the study. Subjects will be encouraged to report any adverse findings during the study whether or not they are related to IP. These can be collected either in an unsolicited fashion without any prompting or in response to a general question such as: "Have you noticed anything different since you started the study; began the IP, etc.?"

All AEs will be captured on the appropriate case report form (CRF). Information to be collected at minimum includes event description, onset, assessment of severity, relationship to IP, and outcome.

The Investigator will record all AEs with start dates occurring any time after informed consent is obtained until 7 (for nonserious AEs) or 30 days (for SAEs) after the last day of study participation. At each study visit, the Investigator will inquire about the occurrence of AE/SAEs since the last visit. Events will be followed for outcome information until resolution or stabilization.

Any medical condition that is present at the time that the subject is screened will be considered baseline and not reported as an AE. However, if the subject's condition deteriorates at any time during the study, it will be recorded as an AE.

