9.7.1.3.3. Prior and Concomitant Medications

Prior and concomitant medications will be coded using the World Health Organization Drug Dictionary (WHODrug) (Version 2022-03, Lagerlund et al., 2020) for anatomical therapeutic chemical (ATC) classification and preferred drug name.

The frequency and percentage of subjects with coded medications will be summarized by treatment group using the Safety Analysis Set. A subject who used multiple medications will be counted only once for each ATC and preferred drug name. Therapeutic Subgroup is sorted alphabetically, and preferred term is sorted by descending frequency overall within each Level 3 term according to:

1. Descending frequency within SY-201, 2.0%;
2. Descending frequency within SY-201, 1.0%;
3. Descending frequency within SY-201, 0.5%;
4. Descending frequency within Vehicle;
5. PT in alphabetical order.

Prior and concomitant medications will be summarized separately. Ocular medications are defined as those medications for which an eye has been specified (OD, OS, or OU). Ocular and non-ocular medications will be summarized separately. Ocular medications will be summarized separately for study eye, non-study eye, and either eye.

Prior medications are defined as any medications that started and stopped prior to the first dose of double-masked study drug. Concomitant medications are defined as any medications that (1) start prior to the first dose of double-masked study drug and stop or are ongoing at or after the date of first dose of double-masked study drug; or (2) start at or after the first dose of double-masked study drug. Medications taken after Visit 6 or withdrawal from the study are not considered concomitant.

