9.7.1.6.1. Adverse Events

AEs are coded using MedDRA Version 25.0. Treatment-emergent adverse events (TEAE) are defined as events that start on or after the first dose administration of double-masked study medication up to and including the last dose of double-masked study medication plus 30 days. Pretreatment adverse events are events that begin prior to first dose administration of double-masked study medication. Ocular AEs are defined as those events for which an eye has been specified (OD, OS, or OU).

Ocular and non-ocular TEAEs will be summarized separately. Ocular TEAEs will be presented by study eye and non-study eye and overall (OU) if an event occurs in either eye.

In all summaries of TEAEs, percentages are calculated based on the number of subjects in each treatment group of the Safety Analysis Set.

Overall summaries of TEAEs by treatment will include:

- the number of TEAEs and serious TEAEs reported;
- the number and percentage of subjects who experienced any TEAE;
- the number and percentage of subjects who experienced any serious TEAE and the reason for seriousness;
- the number and percentage of subjects with any TEAE by worst severity and worst relationship.
- the number and percentage of subjects with any TEAEs leading to discontinuation of double-masked study drug;
- the number and percentage of subjects with any TEAEs leading to study termination.

Summaries of the frequency and percentage of subjects with TEAEs by SOC and preferred term by treatment group will include:

- All TEAEs by SOC and preferred term;
- All TEAEs by SOC, preferred term, and maximum severity;
- All TEAEs by SOC, preferred term, and maximum relationship.

System organ class (SOC) will be sorted alphabetically, and preferred term (PT) within each SOC will be sorted by overall descending order of frequency according to the following rules in order:

1. Descending frequency within SY-201, 2.0%;
2. Descending frequency within SY-201, 1.0%;
3. Descending frequency within SY-201, 0.5%;
4. Descending frequency within Vehicle;
5. PT in alphabetical order.

Subjects are counted only once for each SOC and PT. In summaries of maximum severity and maximum relationship, subjects with multiple occurrences of events will only be counted once at the maximum severity/relationship per SOC and PT.

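### The SAP's partial start-date rule ignores a known earlier stop date, so records that ended before double-masked dosing can be tabulated as treatment-emergent or concomitant

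*SAP*

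**What the plan says.** SAP 9.7.1, Missing Dates, covers medications and adverse events together. A query comes first: "Missing dates that occur for prior or concomitant medications or adverse events will be queried for a date". If the query fails, a partial start date is handled as follows: "if the given year (or year-month) is the same as study drug administration, the start date will be imputed as study drug administration date". Otherwise the missing parts are set to the first day of the month or year. The stop-date bullet has the only cap in the section, and that cap applies to imputed stop dates: "If this creates a date after discontinuation/completion, the date of discontinuation/completion will be used". The use of the result is limited: "Imputed dates will only be used to classify events or medications, such as occurring before or after the start of treatment". Imputed dates appear in tables, and listings keep the dates as collected.

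The classes that these dates feed are defined elsewhere in the SAP:

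- Section 9.7.1.6.1 defines treatment-emergent events as "events that start on or after the first dose administration of double-masked study medication", up to 30 days after the last dose. The complement is also set by the start date: "Pretreatment adverse events are events that begin prior to first dose administration of double-masked study medication".
- Section 9.7.1.3.3 requires both dates for the prior class: "Prior medications are defined as any medications that started and stopped prior to the first dose of double-masked study drug". A medication is concomitant under its second limb if it starts at or after the first double-masked dose, with no condition on when it stopped.

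Protocol 8.2.1 puts run-in events into the database: "The Investigator will record all AEs with start dates occurring any time after informed consent is obtained". Consent is at Visit 1, 14 days before randomization. Protocol 5.5 has medications recorded from 45 days before Visit 1.

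**The concern.** When the timing of an event is uncertain, counting it as on-treatment is a usual and defensible choice. The difficulty is a record whose timing is not uncertain. If the stop date is known and falls before the first double-masked dose, the event or medication must have started before that dose as well. The SAP rule still moves the start to the dose date whenever the known month or year matches. The record then begins after it ended, and the definitions above put it in the wrong table.

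What is at stake is the accuracy of the treatment-emergent and prior/concomitant summaries. Ocular safety is part of the primary objective, and arms are planned at 50 subjects. One subject wrongly added to a table row moves that arm's incidence by 1/50 = 2 percentage points, provided the subject has no other event counted in that row.

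**Working it through.** The plan gives no figure on this point, so the check is first one of logic and then one of reach.

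**Anchor.** The start-date bullet refers to study drug administration without saying double-masked. The definitions in 9.7.1.3.3 and 9.7.1.6.1 both turn on the first double-masked dose, so I read the anchor that way.

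**Test records.** Assume for illustration a first double-masked dose on 20 June 2022, so Visit 1 and consent fall on 6 June (20 − 14).

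| Record | Start as collected | Known stop | Start under the SAP rule | Class under the SAP rule | Class if start is no later than stop |
|---|---|---|---|---|---|
| Run-in adverse event | June 2022 | 12 June | 20 June, 8 days after stop | Treatment-emergent | Pretreatment |
| Medication | June 2022 | 10 June | 20 June, 10 days after stop | Concomitant | Prior |
| Medication | 2022 only | 15 May | 20 June, 36 days after stop | Concomitant | Prior |
| Control medication | May 2022 | 12 June | 1 May | Prior | Prior |

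The first three records get an impossible start and the wrong class. The control is right either way, because its month differs from the first-dose month. Any start on or before the known stop gives the right class, so it does not matter whether the start is capped at the stop or set to the earliest possible date. Under the second option the three starts become 6 June (the later of 1 June and consent), 1 June and 1 January.

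**Reach of the rule.** Assume first-dose dates spread evenly over four calendar years: 1,461 days, 48 months.

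- *Run-in, 14 days.* A first dose on day *j* of a month (*j* = 1 to 14) has 15 − *j* run-in days in the previous month, which sums to 14 + 13 + … + 1 = 105 per month. There are 1,461 × 14 = 20,454 run-in days in all.
  - Same month: 1 − (48 × 105)/20,454 = 1 − 5,040/20,454 = 0.754.
  - Same year: 1 − (4 × 105)/20,454 = 1 − 420/20,454 = 0.979.
- *Medication look-back, 45 + 14 = 59 days.* There are 1,461 × 59 = 86,199 look-back days.
  - Same month: a first dose on day *j* has *j* − 1 such days, or *L*(*L* − 1)/2 in a month of *L* days. The total is 28 × 465 + 16 × 435 + 3 × 378 + 406 = 21,520, and 21,520/86,199 = 0.250.
  - Same year: 1 − 4 × (59 × 60/2)/86,199 = 1 − 7,080/86,199 = 0.918.

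These are shares of calendar days on which a start would match the first-dose month or year. They carry no information on how often a date stays partial or how often the stop date is known and earlier, and both are needed for an error.

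**The case against.** The case against making much of this is strong, and most of it stands.

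- **The affected set is narrow.** The start must be partial, the query must fail, the known part must match the first dose, and the stop must be known to precede it. Run-in events are asked about at Visit 2, when the period to recall is only 14 days. Medications begun in an earlier year are imputed into that year and are classified correctly. The documents do not show that even one record would be affected.
- **The direction is conservative and the rule is common to all arms.** It adds treatment-emergent events and does not hide them. It matches the SAP's practice of tabulating missing severity as severe and missing relationship as related. No statistical safety comparisons are planned unless otherwise specified, and listings keep the collected dates.
- **A programmer might override it.** A stop before first dose implies a start before first dose, so the prior-medication definition is met in substance. That helps for medications, although the imputed date also satisfies the second concomitant limb. It does not help for adverse events, whose class never refers to the stop date.
- **The anchor could be read as the run-in dose.** These records would then be classified correctly. The fault would change direction, however. An adverse event that began after 20 June with the day missing would be set to 6 June, classed as pretreatment, and left out of the treatment-emergent tables. The wording needs settling on either reading.

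A reader might infer from the 75% and 98% that most run-in events with a missing start day or month would be misclassified. The documents do not support that: without a known earlier stop date, moving the start is legitimate caution. A reader might also infer that properly washed-out medications would appear as eligibility failures. Eligibility is decided at Visits 1 and 2 against the criteria, and the SAP plans a separate listing of violations. The imputed-date tables play no part in either.

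**Conclusion.** The point holds in a limited form. With the first double-masked dose as anchor, the rule gives a demonstrably wrong class to any adverse event or medication that has an unresolved partial start matching the first-dose year or year-month and a stop date known to precede that dose. The stated rule is wrong for those records; it is not merely short on detail. For records with an unknown or later stop date it is acceptable and should stay.

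The number of affected records cannot be derived from the documents and is probably small, because dates are queried first. The consequence is confined to the treatment-emergent and prior/concomitant tables. No efficacy estimate, p-value or step of the testing hierarchy changes. The conclusion rests on the anchor reading given above. The reach figures also assume evenly spread first-dose dates. This is a minor correction, worth making because it is almost free.

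**What to change.** Amend the start-date bullet in SAP 9.7.1 in two ways:

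1. Name the anchor as the first dose of double-masked study drug.
2. Add this exception: *unless the known complete or partial stop date shows that the event or medication ended before the first double-masked dose, in which case the missing parts are imputed as the earliest date consistent with the known parts (not before consent for adverse events).*

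A partial stop date counts only where it settles the matter, for example a stop month earlier than the first-dose month. A stop month equal to the first-dose month with the day missing leaves the timing open, and the existing convention applies.

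The cost is one clause in the SAP and one line of derivation code. No new data are needed. A programming check that lists every record whose imputed start is later than its recorded stop would show how many are affected.
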